6.3.3.10 MBS Freedom at 2 Hours Postdose During the DBT Phase

MBS freedom at a single time point postdose is defined as the MBS reported on study before dosing that is absent at that time point, e.g., subjects who report nausea as the MBS before dosing and have nausea absent at 2 hours postdose. The MBS before dosing is reported as nausea, phonophobia, or photophobia. Symptom status is reported postdose as present or absent for each symptom (nausea, phonophobia, and photophobia).

The percentage of subjects with MBS freedom at 2 hours postdose during the DBT Phase is compared between treatment groups using analogous methods as the main analysis of the primary endpoint with NC=F and RM=F (see Section 6.3.2.1). These results are presented together in the same table as those for MBS freedom over time during the DBT Phase (see Section 6.3.5.1).

6.3.4 Other Secondary Efficacy Endpoints

6.3.4.1 Change From Historical Baseline in Number of Migraine Days per Month During the OLE Phase

Analyses are based on the OLE migraine analysis set, i.e., subjects in the OLE efficacy analysis set with time in the OLE Phase ≥ 14 days.

Migraine days during the OLE Phase are defined in Section 9.2.2.

Months in the OLE Phase are defined as follows:

- Month 1: ≤ 4 weeks; OLE days 1 to 28
- Month 2: >4 to ≤ 8 weeks; OLE days 29 to 56
- Month 3: >8 to ≤ 12 weeks; OLE days 57 to 84.

See Section 7.3 for OLE days.

Migraine headache pain intensity categories are (1) total (i.e., none, mild, moderate, severe, or not reported) or (2) moderate or severe.

The number of total migraine days per month in the OLE Phase analysis period is examined relative to total historical baseline, defined as the number of migraine days per month of any pain intensity in the 3 months prior to screening from the Migraine History CRF.

The number of moderate or severe migraine days per month in the OLE Phase is examined relative to moderate or severe historical baseline, defined as the number of moderate to severe migraine days per month in the 3 months prior to screening from the Migraine History CRF.

The number of migraine days per month is prorated to 28 days and derived as follows:

- Month (i.e., 4-week interval) in the OLE Phase analysis period: $28 \times (\text{total number of migraine days in the month}) / (\text{time in the month})$. Subjects must have time in the specified month ≥ 14 days to be evaluable.
 - Time in Month X of the OLE Phase is defined as $\text{maximum}(\text{minimum}[Y, 28], 0)$, where $Y = \{\text{time in the OLE Phase}\} - (28 \times [X - 1])$ days and $X = 1, 2, \text{ or } 3$.
 - Time in the OLE Phase (days) is defined in Section 6.2.6.1.
- Overall OLE: $28 \times (\text{total number of migraine days in the OLE Phase analysis period through OLE day 84}) / \text{minimum}(\text{time in the OLE Phase}; 84 \text{ days})$.

The table of values and changes (both absolute and percent) from the historical baseline in the number of migraine days per month in the OLE Phase is provided for the OLE migraine analysis set, and summaries parameters descriptively as continuous variables (including 2-sided normal 95% CIs for mean change) by treatment group/OL rimegepant and overall and by headache pain intensity (total; moderate or severe) in each month of the OLE Phase and overall OLE. Headache pain intensity categories are (1) total (none, mild, moderate, severe, or not reported) and (2) moderate or severe. Results support other secondary objective #2.

6.3.4.2 Percentages of Subjects With Reduction From Historical Baseline in Number of Migraine Days per Month During the OLE Phase

Analyses are based on the OLE migraine analysis set.

Migraine days per month during the OLE Phase and the overall OLE are defined in Section 6.3.4.1.

In analyses by months, subjects must (1) achieve the reduction criterion from historical baseline in the number of migraine days, (2) have time in the specified month ≥ 14 days to be evaluable, and (3) have historical baseline number of migraine days per months > 0 to be classified as responders in the specified month. Otherwise, subjects are classified as failures in the specified month.

In analyses of the overall OLE, subjects must (1) achieve the reduction criterion from historical baseline in the number of migraine days in the overall OLE, and (2) have historical baseline number of migraine days per months > 0 to be classified as responders. Otherwise, subjects are classified as failures.

The frequency table of percentage reductions from historical baseline in the number of migraine days per month in the OLE Phase is provided by treatment group/OL rimegepant and overall and by headache pain intensity (total; moderate or severe) in each month of the OLE Phase and overall OLE (see Section 6.3.4.1 for months), and displays the following reduction categories:

$\geq 30\%$, $\geq 50\%$, $\geq 75\%$, and 100%. Percentages are calculated against the number of subjects in the OLE migraine analysis set at each month and overall OLE. Results support other secondary objective #3.

6.3.5 Exploratory Efficacy Endpoints

Any p-values presented for exploratory efficacy endpoints during the DBT Phase are for descriptive purposes only, and not included in the hierarchical testing.

6.3.5.1 Efficacy at All Scheduled Time Points Postdose During the DBT Phase

Analyses are based on the DBT efficacy analysis set.

The table of efficacy at each planned time point from 15 minutes through 48 hours postdose during the DBT Phase is provided separately for each of the following efficacy endpoints: pain relief, pain freedom, MBS freedom, return to normal function, photophobia freedom, phonophobia freedom, and nausea freedom. Results support exploratory objectives #3 through #9.

At each planned time point postdose, the percentage of subjects achieving the endpoint during the DBT Phase is compared between treatment groups using analogous methods as the main analysis of the primary endpoint with NC=F and RM=F (see Section 6.3.2.1). For endpoints defined below, “rescue medication” denotes DBT rescue medication.

The line plot of pain relief over time during the DBT Phase displays percentage of subjects achieving pain relief on the y-axis versus time in minutes on the x-axis by treatment group. Error bars denote ± 1 ASE.

Let X denote a planned time point postdose: 15, 30, 45, 60, or 90 minutes; 2, 3, 4, 6, 8, 24, or 48 hours.

Pain Relief Over Time

At time point X, subjects who meet both of the following criteria are classified as responders:

- Migraine headache pain intensity of none or mild at X, i.e., in the X analysis window
- No rescue medication taken at or before the migraine headache pain intensity measurement in the X analysis window (see Section 7.5).

At time point X, subjects who are not responders are classified as failures. Failure criteria include any of the following:

- Rescue medication taken at or before X (RM=F; see Section 7.5)
- Moderate or severe migraine headache pain intensity at X
- Missing migraine headache pain intensity at X (NC=F).

Pain Freedom Over Time

At time point X, subjects who meet both of the following criteria are classified as responders:

- Migraine headache pain intensity of none at X, i.e., in the X analysis window
- No rescue medication taken at or before the migraine headache pain intensity measurement in the X analysis window (see Section 7.5).

At time point X, subjects who are not responders are classified as failures. Failure criteria include any of the following:

- Rescue medication taken at or before X (RM=F; see Section 7.5)
- Mild, moderate, or severe migraine headache pain intensity at X
- Missing migraine headache pain intensity at X (NC=F).

MBS Freedom Over Time

At time point X, subjects who meet both of the following criteria are classified as responders:

- MBS reported before DB study drug dosing that is absent at X, i.e., in the X analysis window
- No rescue medication taken at or before the MBS status measurement in the X analysis window (see Section 7.5).

At time point X, subjects who are not responders are classified as failures. Failure criteria include any of the following:

- Missing MBS before DB study drug dosing (see Section 7.4.2)
- Rescue medication taken at or before X (RM=F; see Section 7.5)
- MBS present at X, e.g., nausea reported as MBS before DB study drug dosing and nausea status of present in the X analysis window
- Missing MBS at X (NC=F), e.g., nausea reported as MBS before DB study drug dosing and missing nausea status in the X analysis window.

Return to Normal Function Over Time

This endpoint is evaluated in the subset of subjects with functional disability at the time of DB study drug dosing (see Section 6.3.3.3).

At time point X, subjects who meet both of the following criteria are classified as responders:

- Functional disability level of normal at X, i.e., in the X analysis window
- No rescue medication taken at or before the functional disability level measurement in the X analysis window (see Section 7.5).

At time point X, subjects who are not responders are classified as failures. Failure criteria include any of the following:

- Rescue medication taken at or before X (RM=F; see Section 7.5)
- Functional disability level of mildly impaired, severely impaired, or requires bedrest at X
- Missing functional disability level at X (NC=F).

Freedom From Photophobia, Phonophobia, or Nausea Over Time

Symptom freedom at a single time point postdose is defined as a symptom status of absent at that time point for the subset of subjects with symptom status of present at the time of dosing.

These endpoints are evaluated in the DBT efficacy analysis set with symptom status of present at the time of DB study drug dosing, e.g., nausea freedom is evaluated for subjects with nausea status of present at the time of DB study drug dosing.

For symptom freedom at X, subjects who meet both of the following criteria are classified as responders:

- Symptom status of absent at X, i.e., in the X analysis window
- No rescue medication taken at or before the symptom status measurement in the X analysis window (see Section 7.5)

For symptom freedom at X, subjects who are not responders are classified as failures. Failure criteria include any of the following:

- Rescue medication taken at or before X (RM=F; see Section 7.5)
- Symptom status of present at X
- Missing symptom status at X (NC=F).

6.3.5.2 Time to Migraine Headache Pain Relief Through 48 Hours Postdose During the DBT Phase

Pain relief during the DBT Phase is defined in Section 6.3.2.

Time to migraine headache pain relief through 48 hours postdose is assessed by treatment group as follows:

- Kaplan-Meier table and plot using the following postdose time intervals: 0 to ≤15, >15 to ≤30, >30 to ≤45, >45 to ≤60, >60 to ≤90, >90 to ≤120, >120 to ≤180, >180 to ≤240, >240 to ≤360, >360 to ≤480, >480 to ≤1440, >1440 to ≤2940, and >2940 minutes. The Kaplan-Meier plot displays the percentage of subjects with migraine headache pain relief through 48 hours postdose on the y-axis versus time in minutes on the x-axis.
- Time-to-event distribution table (minutes), including a log-rank p-value (rimegepant versus placebo).

See Section 6.1.1.1 for time-to-event plot and table attributes. Results support exploratory objective #11.

Subjects are considered to have an event if (1) pain relief is achieved at ≥ 1 time point postdose in the DBT Phase, and (2) the first postdose eDiary finding date/time at which pain relief is achieved is before the imputed first DBT rescue medication date/time, if not missing (see Section 7.1).

Otherwise, subjects who do not have an event are censored at the earlier of the following: (1) upper bound of the 48-hour analysis window + 1 minute (i.e., 2941 minutes); (2) time from the DB study drug date/time to the imputed first DBT rescue medication date/time in minutes; (3) time from the DB study drug date/time to the last postdose eDiary finding date/time with nonmissing migraine headache pain intensity measurement in minutes.

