5 SAMPLE SIZE, POWER, AND TYPE I ERROR

It is anticipated that about 90% of the 300 subjects randomized to each treatment group will have a migraine in the allotted time period of the DBT Phase, resulting in approximately 270 subjects evaluable for efficacy in each treatment group.

The sample size calculation is based on pooled results from Phase 3 single-dose migraine studies C4951054 (BHV3000-301), C4951055 (BHV3000-302), and C4951056 (BHV3000-303). Pooled response rates for migraine headache pain relief at 2 hours postdose were 57.9% for rimegepant 75 mg and 43.9% for placebo in these studies.

A total sample size of 540 evaluable subjects (270 per treatment group) will provide approximately 90% power for the primary endpoint of migraine headache pain relief at 2 hours postdose in the DBT Phase. This is based on a chi-square test with a 2-sided alpha level of 0.05, and assumes that the true response rates in the subjects unsuitable for triptan use is equivalent to the overall pooled response rates above.

Type 1 error is controlled using a 2-sided alpha level of 0.05 and hierarchical testing. First, the significance of the primary endpoint is evaluated at the 2-sided alpha level of 0.05 for rimegepant versus placebo. If the primary endpoint is not significant (i.e., $p\text{-value} > 0.05$), then any further tests on key secondary endpoints will have p-values presented only for descriptive purposes. If the primary endpoint is significant (i.e., $p\text{-value} \leq 0.05$), then the key secondary endpoints are tested hierarchically, each at a 2-sided alpha level of 0.05, in the order specified in Section 3.2.2.1. Thus, a key secondary endpoint is tested only if the preceding key secondary endpoint in the hierarchy is determined to be significant (i.e., $p\text{-value} \leq 0.05$). If a test in the hierarchy is not significant, then any further tests on endpoints in the sequence have p-values presented only for descriptive purposes, and no conclusions are drawn from those results.

For testing of other secondary or exploratory endpoints, no attempt is made to adjust for multiplicity. P-values are evaluated at an unadjusted, 2-sided alpha level of 0.05 and presented only for descriptive purposes.

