The raw eDiary dataset has a manual DCF study medication date parameter (MDOSDAT) with a value that is entered by YPrime into the Manual DCF Study Medication question category. The data are provided from manual DCFs by sites on days subjects took study medication without using the eDiary.

For each manual DCF date record with distinct eDiary finding date/time, it is assumed that the subject took 1 tablet of study drug for that record.

The manual DCF medication date is not used by the eDiary to collect postdose data.

7.4.2 eDiary Migraine Characteristics

The following migraine characteristics parameters are collected in the Migraine question category (1) at the time of dosing during the DBT Phase and OLE Phases, and (2) at planned

time points postdose from 15 minutes through 48 hours (e.g., 15, 30, 45, 60, and 90 minutes; 2, 3, 4, 6, 8, 24 and 48 hours) during the DBT Phase for a single migraine attack:

- Migraine headache pain intensity (none, mild, moderate, severe)
- MBS (nausea, phonophobia, photophobia). Collected only before dosing (i.e., when there is a “no” response to the question about study medication already taken) during the DBT Phase.
- Nausea status (present, absent)
- Nausea intensity (mild, moderate, severe), if nausea status is present
- Phonophobia status (present, absent)
- Phonophobia intensity (mild, moderate, severe), if phonophobia status is present
- Photophobia status (present, absent)
- Photophobia intensity (mild, moderate, severe), if photophobia status is present
- Functional disability level (normal, mildly impaired, severely impaired, requires bedrest)
- Aura preceding or accompanying headache status (yes, no). Collected only at the time of dosing.

During the OLE Phase, the eDiary also collects migraine headache pain intensity regardless of study drug dosing.

Note that parameters collected “at the time of dosing” or without dosing in the Migraine question category have missing planned time point (see Section 7.4.1.1).

During the DBT Phase, the eDiary allows subjects to report 1 set of migraine characteristics parameters per planned time point.

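### MBS freedom (key secondary endpoint 10) credits subjects whose named symptom was recorded absent at dosing, and fails subjects with no predose MBS; neither group informs the endpoint

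*SAP*

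**What the plan says.** Protocol 3.2.1 (endpoint 10) and SAP 6.3.3.10 define MBS freedom by two facts: the MBS was reported before dosing, and that symptom is absent at 2 hours. The operational rule is in SAP 6.3.5.1. A responder has "MBS reported before DB study drug dosing that is absent at X, i.e., in the X analysis window" and has taken no rescue medication by that measurement. The failure criteria include "Missing MBS before DB study drug dosing (see Section 7.4.2". Neither section refers to the status of the named symptom at dosing.

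SAP 7.4.2 describes the eDiary item as "MBS (nausea, phonophobia, photophobia). Collected only before dosing", meaning when the subject answers that study medication has not yet been taken. No option for having no such symptom is listed. Nausea, phonophobia and photophobia status are recorded separately at dosing, and intensity is asked only when status is present. SAP 7.4.1.1 accepts retrospective dose entries. A qualifying attack (SAP 9.3.1) needs moderate or severe pain and no other medication taken; it needs neither an associated symptom nor an MBS.

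For photophobia, phonophobia and nausea freedom, SAP 6.3.5.1 says: "These endpoints are evaluated in the DBT efficacy analysis set with symptom status of present at the time of DB study drug dosing". Return to normal function is likewise limited to subjects with functional disability at dosing. The protocol names a subset for endpoints 3 to 5 but none for endpoint 10.

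**The concern.** Two kinds of subject can enter this endpoint with a result fixed largely by the rule.

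- **Named symptom absent at dosing.** A subject with moderate headache and no associated symptom can be in the DBT efficacy set. If the device makes this subject pick one of three symptoms, and that symptom is still absent at 2 hours, the subject is a responder although nothing changed.
- **No predose MBS.** A subject who takes the tablet first and enters the dose afterwards is not asked for an MBS. This subject fails whatever happens to the symptoms. The same person can be a photophobia-freedom responder and an MBS failure in one report.

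At stake are the response percentage in each arm and the treatment difference for a key secondary endpoint. Little planned output would show how large either group is. The missing-data table (SAP 6.3.1.2) covers postdose data only, the compliance and deviation categories (SAP 6.2.6.2 and 9.1) do not count dosing without an MBS, and the sensitivity analyses concern the primary endpoint only. The table of migraine characteristics at dosing (SAP 6.2.5.2) and the by-subject listing (SAP 6.3.1.1) would let a reader find missing MBS. No planned table crosses the named MBS with its status at dosing.

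**Working it through.** **1. The plan's own figure.** SAP section 5 gives power for pain relief only: "will provide approximately 90% power for the primary endpoint of migraine headache pain relief at 2 hours postdose in the DBT Phase", from rates of "57.9% for rimegepant 75 mg and 43.9% for placebo in these studies", 270 per group and two-sided alpha 0.05. With p̄ the mean of the two rates,

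power = Φ{ [ (p1 − p0) − 1.96·√(2p̄(1 − p̄)/n) ] / √[(p1(1 − p1) + p0(1 − p0))/n] }.

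Putting in the numbers: (0.140 − 1.96 × 0.04303)/0.04260 = 1.307, so power is 90.4%. The stated figure reproduces, and this point does not affect it. The documents state no rate or power for MBS freedom.

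**2. Inputs for MBS freedom.** From the documents: n = 270 per group and alpha 0.05. Assumed, because no document gives them:
- p = MBS freedom among assessable subjects: 40% rimegepant, 28% placebo (difference 12.0 points);
- q = share whose named symptom is absent at dosing;
- m = share with no predose MBS;
- c = share of group q counted as responders at 2 hours: 90% in both arms.

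**3. Formulas.**
- Rate under the current rule: (1 − q − m)·p + q·c. With q, m and c equal across arms, c cancels and the difference is (1 − q − m)(p1 − p0).
- Rate if group q is removed and missing MBS stays a failure: (1 − q − m)·p/(1 − q), with n = 270(1 − q).
- Rate if both groups are removed: p, with n = 270(1 − q − m).

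**4. Results with equal shares.**

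| q | m | Current rule: rates | Difference (points) | Group q removed, missing = failure | Both removed |
|---|---|---|---|---|---|
| 0 | 5% | 38.0% vs 26.6% | 11.4 | 11.4 | 12.0 |
| 3% | 0 | 41.5% vs 29.9% | 11.6 | 12.0 | 12.0 |
| 5% | 5% | 40.5% vs 29.7% | 10.8 | 12.0 × 0.90/0.95 = 11.4 | 12.0 |
| 10% | 10% | 41.0% vs 31.4% | 9.6 | 12.0 × 0.80/0.90 = 10.7 | 12.0 |

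For q = m = 5% under the current rule: 0.90 × 0.40 + 0.05 × 0.90 = 0.405 and 0.90 × 0.28 + 0.05 × 0.90 = 0.297.

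Power in that row, by the formula in step 1:
- current rule: (0.108 − 1.96 × 0.04108)/0.04081 = 0.67, about 75%;
- group q removed, missing = failure (n about 256 per group): about 79%;
- both removed (n = 243): about 80%.

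**5. Other assumed rates.** With 40% vs 30% and c = 85%, q = m = 5% gives 9.0 points and 58.8% power under the current rule, against 10.0 points and 63.8% with both groups removed. At q = 0, m = 5% the powers are 65.0% and 66.1%. Over rate pairs of 25/35%, 30/40% and 35/47% (placebo/rimegepant), with m from 0 to 15% and q from 0 to 10%, removing both groups recovers 0 to about 12 percentage points of power.

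**6. Unequal shares.** With 40% vs 30%, q = 0, and missing MBS of 8% on rimegepant and 4% on placebo, the difference is 0.92 × 0.40 − 0.96 × 0.30 = 8.0 points. With the shares reversed it is 0.96 × 0.40 − 0.92 × 0.30 = 10.8 points.

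**The case against.** **The first group may be empty.** Protocol 6.4.2 asks for the current MBS before dosing, so a symptom named there should be one the subject has. The eDiary logic sits in vendor documents that the SAP cites but that were not available, and it may block choosing an absent symptom. This stands as a limit on size: the SAP's silence about branching does not show that the device allows the contradiction. It does not remove the gap in the rule.

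**The second group is handled by an open, conservative convention.** Missing predose MBS is listed as a failure, consistent with missing = failure elsewhere. Protocol Table 1 tells subjects to take the drug only after the predose entries. Entries made too late for the 2-hour window (SAP Table 7: after 1 h 55 min, before 2 h 16 min) would fail anyway, so the added effect is smaller than the share of retrospective entries. This stands.

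**Restriction is not why the sibling endpoints keep retrospective entrants.** A reader might infer that limiting those endpoints to subjects with the condition present solves both problems. It solves only the first. Retrospective entrants stay in because symptom status and functional disability are collected at dosing whichever way the dose is entered; only the MBS item is withheld from them.

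**Dropping missing MBS from the main analysis is not a clean remedy.** Retrospective entry happens after dosing and could be related to response. Excluding those subjects conditions on postdose behaviour, so it belongs in a supportive analysis.

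**Conclusion.** The point holds in a limited form. The rule credits a symptom recorded absent both at dosing and at 2 hours, and it fails subjects who were never asked. Sibling endpoints in the same section already apply the presence condition, and the documents give no reason for leaving it out here.

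With equal shares by arm the cost is dilution by (1 − q − m): 12.0 to 11.4 points if only missing MBS occurs, at 5%, and to 10.8 points at 5% and 5%. The response rates, the shares and c are all assumptions. A 20% loss of effect needs 10% and 10%, which no document supports.

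A reader might infer that both groups always shrink the difference. That requires equal shares by arm; step 6 shows movement in either direction. A reader might also infer an inflated type I error. With equal shares, and c equal in both arms, a null difference stays null. MBS freedom is also last of the ten key secondary endpoints, so no later test depends on it.

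**What to change.** In SAP 6.3.3.10 and 6.3.5.1:

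1. Among subjects with a reported MBS, evaluate MBS freedom only where that symptom's status is present at DB dosing. This is a predose filter and matches the sibling endpoints.
2. Keep NC=F and RM=F for postdose data, and keep missing predose MBS as failure in the main analysis.
3. Add a supportive analysis that also excludes subjects with missing predose MBS, and a row under the current all-subjects rule.
4. Report by arm the number with the named symptom absent at dosing and the number with no predose MBS.
5. Align Protocol 3.2.1 endpoint 10 with the SAP.

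If treatment is already unblinded, present the restricted analysis as supportive only and leave the prespecified rule as the main analysis.

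The cost is SAP and protocol wording, one filter and a few table rows, all on data already collected. The main analysis has a slightly smaller denominator, and the supportive analysis conditions on retrospective entry, which should be stated beside it.
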